### **3.0. Objectives and Hypothesis**

#### **3.1 Primary Objective**

The proposed trial is intended to test the effectiveness of [name]'s and Schilling's five-session safer sexual skills building group (SSB) intervention for female patients in MMTP or in drug-free outpatient treatment. The effects of this intervention will be compared to those of 1 standard group HIV education session (HE). There will be one primary outcome: number of unprotected (vaginal or anal) penetrative intercourse occasions within the prior 3 months. It is hypothesized that women in the SSB intervention will decrease their number of unprotected penetrative sexual behaviors at 3 and 6 month follow up assessments significantly more than women in the HIV education intervention.

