exactly correct), we can compute the non-central parameter and thus determine the power of the test.

Power of the test for difference between the two interventions with respect to number of unprotected sex occasions is computed for a range a values of the difference and the associated covariance parameters. As described in Section 8.4.2: Sexual and Sexual Risk Behavior Assessment, following state-of-the-art practices in HIV risk behavior intervention research, our primary outcome variable is number of unprotected sex occasions in the past 3 months. For purposes of our sample size and statistical power considerations, we have drawn on the HIV prevention intervention findings, among a comparable population of at-risk-for-HIV, inner city women, of Ehrhardt et. al. (2002). They reported an average of 17 unprotected sexual occasions in the 3 months prior to intervention in their sample. In our examination of differences between the two intervention conditions of our study, we have considered 3 levels of differences from this average. In particular, we have considered: (1) A difference of 2 unprotected sex occasions, or 15 versus 17; (2) A difference of 1.5, of 15.5 versus 17; and (3) a difference of 1, or 16 versus 17. In as much as a single occasion of unprotected sex can result in HIV infection, these differences are considered clinically significant. It should be noted that Ehrhardt et al. (2002) article did not present actual averages for their 3 intervention conditions. We have obtained unpublished averages from the authors, as follows: (1) Baseline: Control (0 intervention sessions):17.4; 4-session intervention: 13.7; 8-session intervention: 20.9; and (2) Three-month follow-up: Control: 19.5; 4-session intervention: 13.17; 8-session: 11.23.

Difference in the number of the of unprotected sex occasions:

- 1) Experimental intervention mean=15, control intervention mean=17
- 2) Experimental intervention mean=15.5, control intervention mean=17
- 3) Experimental intervention mean=16, control intervention mean=17

Parameters related to the covariance:

The correlation between repeated observations on a subject is  $\rho_1$ . The correlation between subjects in the same therapeutic group (cluster) is  $\rho_2$  and  $\rho_2 \leq \rho_1$ . The correlation between subjects from different therapeutic groups within the same CTP (strata) is  $\rho_3$  and  $\rho_3 \leq \rho_2$ .

- 1) within subject correlation:  $\rho_1 = 0.4, 0.6, 0.8$

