## **11.5 Analytic Plan**

### **11.5.1 Testing and estimation**

All testing will be two-sided and significance will be judged at level  $\alpha=0.05$ . Effects will be reported with point estimate and 95% confidence intervals in addition to p-values.

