## 11.6 Analysis of specific hypotheses

### 11.6.1 Primary hypothesis

Hypothesis 1: SSB intervention will significantly outperform the HE condition with respect to decreasing the number of penetrative intercourse occasions that are unprotected.

The following marginal model for outcome of count will be used to test this hypothesis:

$$(1) \quad \log E(Y_{ijkt}) = \beta_0 + \beta_1 X_{ijk} + \beta_2 t + \beta_3 X_{ijk} t + \gamma_1 Z_{1ijk} + \gamma_2 Z_{2ijk}$$

where  $Y_{ijkt}$  is the value of the primary outcome measure at time  $t$ ,  $t=0$  for 3 months post intervention and  $t=1$  for 6 months post-intervention, for the  $i^{th}$  subject in the  $j^{th}$  intervention group (cluster) in the  $k^{th}$  CTP site (strata);  $X_{ijk}$  is intervention indicator ( $X_{ijk}=1$  for the experimental intervention and  $X_{ijk}=0$  for the control intervention);  $Z_{1ijk}$  is the value of the outcome measure prior to intervention;  $Z_{2ijk}$  is the monogamy status prior to intervention. The model parameters will be estimated by GEE (generalized estimating equation) approach that makes use of all available data and takes into account the within site, within treatment group, and within subject correlations in the way insensitive to the specification of correlations.

The regression parameters in this model correspond to intervention effects of interest. For example, statistically significant from 0 parameter  $\beta_3$  indicates that over time the effects of the two study interventions are different;  $\beta_3 < 0$  corresponds to the effect of the experimental intervention increasing over time faster than the effect of the experimental intervention;  $\beta_3 = 0$  corresponds to no difference in the effectiveness of the interventions over time. If  $\beta_3 = 0$ , the parameter  $\beta_2$  estimates the rate of change in the outcome measure from 3 to 6 months post-intervention in the two intervention groups, and the parameter  $\beta_1$  estimates the difference between the experimental and control intervention, which is the same at the two follow-up assessment times.

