We clarify that each parameter in the model corresponds to a distinct question. A statistically significant coefficient for the interaction term ( $\beta_3$ ) will indicate that the intervention effect is different at 3 and 6 months; in this case, different intervention effects will be estimated for 3 and 6 months post intervention. If the interaction term is not significant, the intervention effect will be estimated with the coefficient for the main effect of the intervention,  $\beta_1$ . The coefficient for monogamy status will be used to assess the effect of monogamy, etc. We maintain that no multiple testing adjustment is necessary – with the proposed strategy for testing the hypothesis that the experimental intervention will be superior to the control intervention with respect to number of unprotected sex occasions.

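### Section 11.6.1 lets a preliminary test of beta3 choose the primary estimate and states neither a success rule nor a refit, so its claim that no multiplicity adjustment is needed is unsupported

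*Protocol*

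**What the plan says.** Protocol section 3.1 hypothesises that the skills-building arm (SSB) will reduce unprotected occasions "at 3 and 6 month follow up assessments significantly more than women in the HIV education intervention". Section 11.5.1 sets the error level: "All testing will be two-sided and significance will be judged at level" 0.05.

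Section 11.6.1 fits a marginal log-linear model (1) with terms beta1 X, beta2 t and beta3 X t plus baseline covariates. Time is coded t = 0 "for 3 months post intervention and" t = 1 for 6 months. The log effect is therefore beta1 at 3 months and beta1 + beta3 at 6 months. If beta3 equals zero, the section describes beta1 as the arm difference "which is the same at the two follow-up assessment times".

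The decision path follows. After a significant beta3, "in this case, different intervention effects will be estimated for 3 and 6 months post intervention". Otherwise: "If the interaction term is not significant, the intervention effect will be estimated with the coefficient for the main effect of the intervention". The section closes the matter with "We maintain that no multiple testing adjustment is necessary".

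Section 11.5.4 states that the sample size rests on the same model as the planned analysis.

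**The concern.** Three things are left open or joined wrongly.

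- **Success rule.** After a significant beta3 there are two effects. The text does not say whether one or both must be significant, or how 0.05 is shared between them. Whether the path holds 5% depends on that rule, so the flat denial of any need for adjustment has nothing behind it.
- **Non-significant is read as zero.** The common-effect meaning of beta1 is given for beta3 = 0, but the decision rule applies it when beta3 is merely not significant.
- **Refit.** Nothing says that the interaction is removed before beta1 is read off. If it stays in, beta1 is the 3-month contrast and the 6-month data do not contribute to the estimated effect.

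At stake are the error rate of the only primary hypothesis, and whether the test performed is the one that was powered.

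**Working it through.** **Inputs (section 11.2 and its Tables 1 and 2).** Control mean 17; SSB mean 15, 15.5 or 16; Poisson variance; rho1 = 0.4, 0.6, 0.8; rho2 = 0.10, 0.15; rho3 = 0.05, 0.10; 12 sites. Table 1 has 10 groups of 4 women per site (n = 20 per arm). Table 2 has 5 groups of 8 (2 SSB, 3 control).

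**Step 1: reproduce the stated power.** For a group size m and n women per arm per site, the variance factor of an arm mean averaged over both visits is

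[(1 + rho1)/2 + (m - 1) rho2 + (n - m) rho3] / n,

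with covariance rho3 between arms within a site. First cell of Table 1 (0.40, 0.10, 0.05; 17 vs 16):

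- factor = (0.70 + 0.30 + 0.80)/20 = 0.090
- variance = [0.090 x (16 + 17) - 2 x 0.05 x sqrt(16 x 17)]/12 = (2.970 - 1.649)/12 = 0.1101, so SE = 0.332
- 1/0.332 = 3.014, and Phi(3.014 - 1.960) = **0.854**, against the stated **0.85**

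All 72 cells without over-dispersion in the two tables reproduce within 0.5 point.

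**Step 2: the same cell with beta1 as the 3-month contrast.** Replace (1 + rho1)/2 by 1:

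- factor = (1 + 0.30 + 0.80)/20 = 0.105
- variance = (3.465 - 1.649)/12 = 0.1513, so SE = 0.389
- 1/0.389 = 2.571, and Phi(2.571 - 1.960) = **0.729**

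This value does not depend on rho1. The first three rows of Table 1 for 17 vs 16 fall with rho1 (0.85, 0.81, 0.77), so they cannot describe a single-visit test. Across both tables, 17 vs 16 without over-dispersion, the loss is about 3 to 13 points. For 17 vs 15, 3-month power is at least 0.96 everywhere. For 17 vs 15.5 it is at least 0.90 in Table 1 and 0.798 in the worst over-dispersed cell of Table 2.

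**Step 3: correlation between the visit estimates.** Replace the first term of the factor by rho1 to get the covariance. In the same cell this is (0.40 + 0.30 + 0.80)/20 = 0.075, so the correlation is (2.475 - 1.649)/(3.465 - 1.649) = 0.455. Over the full grid and both designs it runs from 0.33 to 0.88.

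**Step 4: type I error with no effect at either visit.** With equal variances, the average and the difference of the two visit estimates are independent. If the model is refitted after a non-significant beta3,

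error = 0.95 x 0.05 + 0.05 x P(success | beta3 significant).

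Simulation (4 million draws) gives P(either visit significant | beta3 significant) = 0.464 at correlation 0.33 and 0.155 at 0.88. Hence 0.0475 + 0.0232 = 0.071 and 0.0475 + 0.0078 = 0.055.

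| Rule after a significant beta3 | Interaction kept | Refitted |
|---|---|---|
| Either visit may win | 5.4%-6.2% | 5.5%-7.1% |
| Both visits must be significant | 3.9%-4.6% | 4.8% |
| Average of both visits, tested whatever beta3 shows | 5.0% | 5.0% |

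Rejections in favour of SSB only, under the either-visit rule, are 2.7%-3.5% against a nominal 2.5%.

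**Step 5: does a non-significant beta3 show beta3 = 0?** If the effect changes by 0.5 occasion between visits, power to detect it is about 0.23 (rho1 = 0.4) to 0.57 (rho1 = 0.8). It does not.

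**The case against.** A reader might infer that the primary type I error simply exceeds 5%. The protocol does not support that. It says only that two effects will be estimated, and the hypothesis in section 3.1 names both visits, which can be read as requiring both. Under that rule there is no inflation. This part of the objection stands: the excess is conditional on an either-visit rule that the text neither states nor excludes.

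A reader might also count a significant beta3 as proof that SSB is better, which would put the error near 9%-10%. Section 11.6.1 gives beta3 a different question, whether the effect differs between 3 and 6 months, so that figure should not be used.

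Third, a reader might conclude that the powered test is not the test performed. The reference to a main effect, the common-effect description of beta1 and the statement in section 11.5.4 all favour a refit without the interaction. With a refit the power loss disappears, and only the data-chosen path remains. The power loss (interaction kept) and the larger inflation (interaction dropped) are alternatives and cannot both occur.

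Finally, section 11.2 claims sufficient power only for 17 vs 15 and 17 vs 15.5 and concedes somewhat limited power at 17 vs 16. At the first two differences even the 3-month contrast keeps about 0.80 or more. That also stands, and it limits the practical harm.

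**Conclusion.** The point holds in a limited form. The protocol fixes a data-dependent path to its primary estimate, treats a non-significant interaction as absent, omits both the success rule and the refit, and asserts that no adjustment is needed. That assertion is unsupported: it is right if both visits must be significant and wrong if either suffices, with error then between 5.4% and 7.1%. If model (1) is kept as written, beta1 is not the contrast behind the power tables, contrary to section 11.5.4.

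This is a should-fix: the inflation is modest and conditional, and power at the differences called adequate is little affected. The figures assume large-sample normality, equal variance at the two visits, no dropout and no gain from baseline adjustment.

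**What to change.** In section 11.6.1, name one primary test at two-sided 0.05, made whatever beta3 shows: the log rate ratio averaged over 3 and 6 months, beta1 + beta3/2. This is the test that the power tables describe, so its error is 5% and the stated power without over-dispersion applies. Report beta3 and the 3- and 6-month effects as supportive estimates with confidence intervals. Replace the no-adjustment sentence with a statement that there is a single primary test. Section 11.8 defines its null hypothesis through the same coefficient and should be aligned with the chosen contrast.

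The cost is about one paragraph and no participants. The downside is that the visit-specific effects become supportive. If the sponsor wants a claim at each visit, naming both with a stated rule (both required, or an adjusted pair) would also close the gap, but would no longer match the power tables.

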### 11.6.2 Secondary hypotheses

Hypothesis 2: SSB intervention will significantly outperform HE intervention with respect to decreasing the proportion of drugs-or-alcohol-with-sex occasions (of all sex occasions).

Hypothesis 3: SSB intervention will significantly outperform HE intervention with respect to decreasing the proportion of unprotected sex occasions (of all sex occasions).

Hypothesis 4: SSB intervention will significantly outperform HE intervention with respect to increasing perceived self-efficacy to carry out safer sex.

Hypothesis 5: SSB intervention will significantly outperform HE intervention with respect to increasing condom carrying.

Hypothesis 6: SSB intervention will significantly outperform HE intervention with respect to increasing the magnitude of egalitarian gender role beliefs.

Some of these outcome measures could be assumed to follow normal distribution and for them linear mixed effects models will be used test the respective hypotheses. Linear Mixed Effects Models for continuous outcome Y will be employed:

$$(2) \quad Y_{ijkt} = \beta_0 + \beta_1 X_{ijk} + \beta_2 t + \beta_3 X_{ijk} t + \gamma_1 Z_{1ijk} + \gamma_2 Z_{2ijk} + s_k + s_{kt} + c_j + \varepsilon_{it},$$

Here the variables X, Z and t are defined the same as in (1),  $s_k$  is a random effect for strata,  $s_{kt}$  is a random effect for strata by intervention interaction,  $c_j$  is a random effect for cluster and  $\varepsilon_{it}$  is an individual error term and the two error terms associated with the two measurements on the same individual will be correlated. The following assumptions

about the random terms are made:  $s_k \sim N(0, \sigma_s^2)$ ,  $s_{kt} \sim N(0, \sigma_{st}^2)$ ,  $c_j \sim N(0, \sigma_c^2)$ ,  $\varepsilon_{it} \sim N(0, \Sigma)$  and all random terms are independent of each other and  $\Sigma$  is homoskedastic. The estimated variance of the random effects of sites by intervention ( $s_{kt}$ ) will give a measure of the variability of the intervention effects between sites. This can be compared with the estimated variance of the random site effects ( $s_{kt}$ ), which estimates the variability between sites with respect to the efficacy of the control treatment. The estimated variance of the random effects associated with cluster ( $c_j$ ) will be a measure of the variability in the outcome measure associated with intervention group within a CTP site. We anticipate that this variance will be small compared with the between CTP sites variance.

Binary outcome will be analyzed with marginal logistic regression and outcome of count will be analyzed with the marginal model similar to (1). The covariates in these regression models will be specified in the same way as in testing the primary hypothesis. GEE will be used to estimate the parameters in the marginal models.

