The covariance structure for any particular model will be determined by modeling a variety of possible covariance structures. For example, the correlations between repeated measures on an efficacy measure over time will be modeled as auto-regressive correlation of order one or, compound symmetry or, unstructured correlation. Selection of which structure to be used will be based upon review of both Akaike's Information Criteria and Schwarz's Bayesian Criteria. An auto-regressive covariance structure has the property that observations taken close in time are more correlated than observations taken further apart in time. This correlation structure can be combined with either homogeneous or heterogeneous variances of the observations at different times. A compound symmetric covariance structure has the property that all observations are equally correlated, no matter how much time has elapsed between observations. Compound symmetry covariance structure is appropriate for modeling the correlation between subjects within sites and corresponds to a random effect for site. An unstructured covariance has no restrictions on the correlation and the variances of the repeated measurements; however, it does estimate many more parameters than the other two-covariance structures and is often inefficient.

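### Secondary model (2) fixes equal residual variance at 3 and 6 months, against the covariance selection in 11.5.4; with two visits an unstructured matrix costs one parameter

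*Protocol*

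**What the plan says.** Protocol 11.5.4 (Mixed Effects Models) sets a general rule: "The covariance structure for any particular model will be determined by modeling a variety of possible covariance structures". The candidates for the repeated measures are autoregressive of order one, "compound symmetry or, unstructured correlation". On the choice it says: "Selection of which structure to be used will be based upon review of both" the Akaike and the Schwarz criteria. Of the autoregressive structure it adds: "This correlation structure can be combined with either homogeneous or heterogeneous variances of the observations at different times". Of the unstructured matrix it warns that "it does estimate many more parameters than the other two-covariance structures and is often inefficient", but it leaves that matrix on the list.

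Protocol 11.6.2 (Secondary hypotheses) then writes model (2) for outcomes taken as normal. It has random effects for site, site by intervention and cohort, plus an individual error, and it states that "the two error terms associated with the two measurements on the same individual will be correlated". Time is coded as in model (1) of 11.6.1, where t=0 stands "for 3 months post intervention and" t=1 for 6 months; the pre-intervention value enters as a covariate. The assumptions on the random terms end with Σ, which "is homoskedastic. The estimated variance of the random effects of sites by intervention" (the second half of that quote begins a new sentence on another subject).

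**The concern.** Two things do not fit together. First, a homoskedastic Σ, read as equal variance at the two visits, excludes the unstructured and heterogeneous-variance options that 11.5.4 promises for any model. Once it is imposed, the AIC/BIC selection has nothing left to choose between. Second, the caution in 11.5.4 about the number of parameters gives no reason to avoid the unstructured matrix in a model with two visits.

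The stake is the precision attached to effects at a single visit. While the interaction is in model (2), β1 is the 3-month effect and β1+β3 the 6-month effect. If the residual spread differs between visits, one pooled variance makes the interval too narrow at one visit and too wide at the other.

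**Working it through.** **Number of outcome times.** The plan's own power figures confirm two follow-up measurements per woman. For the first row of Table 1 in 11.2 (17 vs 16, no over-dispersion, ρ1=0.40, ρ2=0.10, ρ3=0.05, 60 groups of 4 per arm):

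SE² = (17/60 + 16/60) × {[(1+0.40)/2 + 3×0.10]/4 − 0.05} = 0.55 × 0.20 = 0.11, so SE = 0.332.

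Power = Φ(1/0.332 − 1.96) = 0.854, against the stated 0.85. One follow-up would give 0.730 and three would give 0.897. This figure concerns the primary outcome and is not in dispute.

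**Parameter counts.** Compound symmetry and AR(1) have 2 parameters at any number of visits T; unstructured has T(T+1)/2.

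| T | Compound symmetry | AR(1) | Unstructured |
|---|---|---|---|
| 2 | 2 | 2 | 3 |
| 3 | 2 | 2 | 6 |
| 4 | 2 | 2 | 10 |

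At T=2, AR(1) and compound symmetry are the same matrix (one variance, one correlation, taken as non-negative). Either one with heterogeneous variances is the unstructured matrix.

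**Effect of a pooled variance.** Let r be the ratio of residual SDs between the visits (assumed; no figure in the protocol), with variance 1 at the less variable visit and r² at the other. Further inputs:

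- Pooled variance p = (r²+1)/2.
- Cohort size n = 40/6 = 6.67 (6.3.1: 40 women in 6 cohorts).
- Cohort variance c = p × ICC/(1−ICC). The ICC values 0.10 and 0.15 are borrowed from 11.2, where they were set for the primary outcome.
- The model's variance at either visit is proportional to c + p/n; the true one is c + r²/n or c + 1/n.
- Actual test size = 2[1 − Φ(1.96 × √(model/true))].

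Worked case, r=1.3 and ICC 0.10:

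- p = 1.345, c = 0.1494, model variance = 0.1494 + 0.2018 = 0.3512.
- More variable visit: true variance = 0.1494 + 0.2535 = 0.4029; √ratio = 0.934; size 6.7%.
- Other visit: true variance = 0.1494 + 0.1500 = 0.2994; √ratio = 1.083; size 3.4%.

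| Cohort ICC | More variable visit, r = 1.1 to 1.3 | Other visit, r = 1.1 to 1.3 |
|---|---|---|
| 0.10 | 5.6% to 6.7% | 4.4% to 3.4% |
| 0.15 | 5.5% to 6.4% | 4.5% to 3.7% |
| 0 | 6.1% to 8.0% | 3.9% to 2.3% |

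Site-by-intervention variance is left out; it would dilute the error further.

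**What is not distorted.** With complete data, the variance of the 6-minus-3-month contrast depends on σ3² + σ6² − 2cov. Pooling leaves that sum unchanged because 2p = σ3² + σ6², so the SE of β3 is right. The same argument gives the right SE for a common effect refitted without the interaction. That effect only loses some efficiency: 5–12% of variance at a variance ratio of 1.5, for within-subject correlation 0.4–0.8.

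**Cost of unstructured.** This was simulated with 4,000 runs, 240 women per arm, correlation 0.6, no clustering and truly equal variances. Mean SEs at 3 and 6 months were 0.0912/0.0911 unstructured against 0.0912/0.0912 pooled, with coverage 95.3%/94.9% against 95.3%/94.8%. At a variance ratio of 1.5 (6 months over 3 months), pooled coverage was 97.5%/93.1% and unstructured 95.1%/95.7%; coverage for β3 was 94.8% under both.

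**The case against.** A reader might infer that 11.5.4 rejects the unstructured matrix. It does not: it lists it as a candidate and only warns that it is often inefficient. A reader might also infer that the parameter remark is simply wrong. It is a general remark, and it is fair with three or four visits (6 or 10 parameters against 2). Table 2 of section 8 does schedule the self-efficacy scale and the Bem inventory at four visits. The remark fails only for model (2) as written.

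The word homoskedastic could instead mean the same Σ for all women or for both arms, and then there is no conflict. That reading cannot be excluded. However, Σ is the matrix of one woman's two errors, and 11.5.4 speaks of homogeneous or heterogeneous variances at different times, so equality over time is the natural reading. Either way the clause needs clarifying.

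The strongest objection is that the harm is hypothetical and narrow. Nothing in the protocol suggests that spread differs between the follow-ups. The largest error rates require zero cohort variance, while 11.2 plans on 0.10 or 0.15. Section 11.6.1 reports separate 3- and 6-month effects only if the interaction is significant, and it says so for the primary model; carrying that rule to model (2) is an inference. If β3=0, that section treats β1 as a common effect. All of this stands, and it limits the point without removing the conflict between the sections.

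Detailed covariance choice may also be left to an analysis plan that is not shown. But the protocol has already fixed it here, in two ways that disagree.

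**Conclusion.** The conflict is real on the natural reading of 11.6.2, and the parameter-count caution does not apply to model (2). The consequence depends on unequal residual spread at the two visits, which is an assumption. With SD ratios of 1.1–1.3 and realistic clustering, the visit-specific tests are off by roughly one-half to under two percentage points, in opposite directions at the two visits.

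The documents do not support a wider claim. The primary, binary and count outcomes are analysed by GEE and are untouched. With complete data, neither β3 nor a refitted common effect has a distorted standard error. Nor is the homoskedastic assumption without any saving: it saves one parameter, which is negligible with about 480 women. This is a minor point, worth correcting because the correction costs almost nothing.

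**What to change.** In 11.6.2, replace the homoskedastic clause with: *Σ is an unstructured 2×2 matrix for the 3- and 6-month measurements, common to all women.* In 11.5.4, add that the AIC/BIC selection and the caution on parameter count do not apply to these two-time models, and keep both for models with more visits.

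Deleting or clarifying the homoskedastic clause alone would also reconcile the sections. Naming the unstructured matrix is preferable because it removes a data-driven choice at a price of one parameter.

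The cost is two sentences and one option in PROC MIXED (TYPE=UN), with no new data and no visible loss of precision if the variances are in fact equal.
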